9.1.12 Secondary Analysis

For continuous variables, a summary of these endpoints will be prepared at each specified timepoint and will include an estimate of the mean change from baseline for each treatment group and of the adjusted treatment difference and 95% confidence interval. The between-

treatment comparison will employ a mixed model of repeated measures (MMRM) with treatment as fixed factor and baseline as a covariate.

For categorical variables, a summary of these endpoints will be prepared at each specified timepoint and will include the number and percentage of each category. A chi-square test will be performed. Confidence intervals on the difference between pairwise comparisons of treatments with the placebo group will be computed. These analyses will not be adjusted for study center.

Secondary efficacy analyses will be performed on the FAS population.

The PP population set will be also tested to confirm the robustness of the secondary analyses.

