6.3.6.2 Secondary Analysis

The secondary efficacy endpoints are described in Section 3.2. All secondary efficacy endpoints defined in this section will be analysed as exploratory.

For categorical variables, a summary of these endpoints will be presented at each specified timepoint by treatment group and will include the number and percentage of each category with the 95% CI. A chi-square test or Fisher Exact test, as appropriate will be performed to compare proportions between treatments at each timepoint.

For continuous variables: VAS photophia, Snellen best-corrected visual acuity (BCVA) score and VAS pain score, a summary of these endpoints will be presented at each specified timepoint by treatment group. Change from baseline will be derived and presented in the same way.

For variables: Anterior chamber cell grades, anterior chamber flare grades, severity of signs of ocular inflammation and eye discomfort grades categorical and continuous summary statistics will be presented, changes from baseline will also be derived and will be presented as increase, decrease or not change table. In the same way, a table with 2 categories: Improvement and no improvement (increase+no change) will be presented. A chi-square test or Fisher Exact test will be performed to compare proportions between treatments:

Change from baseline to Day 3		
Anterior Chamber Cell Grade	IMP	Placebo
Decrease (Improvement)	n (%)	n (%)
No change	n (%)	n (%)
Increase (Worsening)	n (%)	n (%)
P value chi-square or Fisher	p-v	value
Improvement	n (%)	n (%)
No Improvement	n (%)	n (%)
	p-v	/alue

No Improvement = increase + no change

For the variables mentioned above, to see the proportion of patients with different grades, a descriptive table like the following will also be built, no statistical inference will be made:

Grade	IMP			Placebo		
Grade	Baseline	Day X	Change	Baseline	Day X	Change
0	n (%)	n (%)	(%)	n (%)	n (%)	(%)

Date: |09-JUL-2021|

Sponsor: Laboratorios Salvat, S.A. Study Code: CLOBOF3-16IA01 NCT No.: NCT04246801

0.5+	n (%)	n (%)	(%)	n (%)	n (%)	(%)
1+	n (%)	n (%)	(%)	n (%)	n (%)	(%)
2+	n (%)	n (%)	(%)	n (%)	n (%)	(%)
3+	n (%)	n (%)	(%)	n (%)	n (%)	(%)
4+	n (%)	n (%)	(%)	n (%)	n (%)	(%)

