Between treatment comparison of the evolution over time will be analysed using a Restricted Maximum Likelihood (REML)-based repeated measures approach (Mixed Model Repeated Measures [MMRM]). The model for analysis will include the change from baseline as a dependent variable, the baseline score as a cavariate, the categorical fixed effects of treatment (IMP, Placebo) and visit and the interaction treatment*visit. An unstructured (co)variance structure will be used to model the within-patient errors. If this analysis fails to converge, alternative covariance structures will be tested. Akaike's information criterion will be used to determine the best fit (smaller AIC).

If it is not possible to apply a MMRM due to the non-normality of the variable, the Mann Whitney Wilcoxon test will be performed.

Secondary efficacy analyses will be performed on the FAS population.

The PP population set will be also tested to confirm the robustness of the secondary analyses.

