6.5 Adjustment for Covariates

Baseline value will be used as a covariate in the MMRM analyses for the continuous secondary efficacy endpoints (see Section 6.3.6).

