
14.2.16.1

14.2.16.2

14.2.17

Sponsor: Laboratorios Salvat, S.A. Study Code: CLOBOF3-16IA01 NCT No.: NCT04246801

14.2.11.5	Change from Baseline to Day 3, Day 8, Day 15 and Day 29 compared to placebo in the severity of ciliary injection. Improvement or no Improvement	FAS non- RM	
14.2.11.6	Change from Baseline to Day 3, Day 8, Day 15 and Day 29 compared to placebo in the severity of ciliary injection. Descriptive table	FAS non- RM	
14.2.11.7	Change from Baseline to Day 3, Day 8, Day 15 and Day 29 compared to placebo in the severity of corneal edema. Improvement or no Improvement.	FAS non- RM	
14.2.11.8	Change from Baseline to Day 3, Day 8, Day 15 and Day 29 compared to placebo in the severity of corneal edema. Descriptive table	FAS non- RM	
14.2.11.9	Change from Baseline to Day 3, Day 8, Day 15 and Day 29 compared to placebo in the severity of keratic precipitates. Improvement or no Improvement	FAS non- RM	
14.2.11.10	Change from Baseline to Day 3, Day 8, Day 15 and Day 29 compared to placebo in the severity of keratic precipitates. Descriptive table	FAS non- RM	
14.2.12	MMRM. Change from Baseline to Day 3, Day 8, Day 15 and Day 29 compared to placebo in the visual analog scale (VAS) photophobia score.	FAS non- RM	
14.2.13	MMRM. Change from Baseline to Day 8, Day 15 and Day 29 compared to placebo in Snellen best.corrected visual acuity (BCVA) score.	FAS non- RM	
14.2.14	MMRM. Change from Baseline to Day 3, Day 8, Day 15 and Day 29 compared to placebo in the VAS pain score.	FAS non- RM	X
14.2.15.1	Change from baseline to Day 3, Day 8, Day 15 and Day 29	FAS	

Sponsor: Laboratorios Salvat, S.A. Study Code: CLOBOF3-16IA01 NCT No.: NCT04246801

14.2.18	Percentage of patients with anterior chamber cell grade of "0" compared to placebo at Day 8. Sensitivity Analysis	FAS non- RM	
14.2.19.1	Proportion of patients with VAS pain score of "0-0.2 cm" (no eye pain) compared to placebo at Day 3, Day 8, Day 15 and Day 29 (FAS non-RM set).	FAS non- RM	X
14.2.19.2	Proportion of patients with VAS pain score of "0-0.2 cm" (no eye pain) compared to placebo at Day 3, Day 8, Day 15 and Day 29 (FAS Set).	FAS	X
14.2.20.1	Proportion of patients with VAS pain score of "0-0.4 cm" (no eye pain) compared to placebo at Day 3, Day 8, Day 15 and Day 29 (FAS non-RM set).	FAS non- RM	X
14.2.20.2	Proportion of patients with VAS pain score of "0-0.4 cm" (no eye pain) compared to placebo at Day 3, Day 8, Day 15 and Day 29 (FAS Set).	FAS	X

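### The MMRM shares one baseline slope across all visits; a baseline-by-visit term is a nearly free refinement that may sharpen the exploratory Day 3 VAS comparisons

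*SAP*

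**What the plan says.** SAP 6.3.6.2 gives the response ("The model for analysis will include the change from baseline as a dependent variable"), the mean model ("the baseline score as a cavariate, the categorical fixed effects of treatment (IMP, Placebo) and visit and the interaction treatment*visit") and the covariance ("An unstructured (co)variance structure will be used to model the within-patient errors"). If the unstructured covariance does not converge, alternatives are compared by AIC. SAP 6.5 adds only that "Baseline value will be used as a covariate in the MMRM analyses for the continuous secondary efficacy endpoints". Protocol 9.1.12 is briefer still, with "treatment as fixed factor and baseline as a covariate", and SAP 6.1 says that the SAP supersedes the protocol's methods. A baseline-by-visit term appears in none of these places.

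The model serves Tables 14.2.12 (VAS photophobia), 14.2.13 (BCVA) and 14.2.14, whose title begins "MMRM. Change from Baseline to Day 3, Day 8, Day 15 and Day 29 compared to placebo in the VAS pain score". SAP 3.2 also refers to a model for the daily diary pain scores. The status is stated in SAP 6.3.6.2: "All secondary efficacy endpoints defined in this section will be analysed as exploratory".

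**The concern.** With change as the response, the coefficient on baseline equals the slope of the visit score on baseline, minus 1. Where nearly everyone is close to 0, the score hardly depends on baseline and the coefficient is close to -1. At Day 3, when scores may still track baseline, it should lie nearer 0. One coefficient cannot serve both. Generalised least squares pulls it towards the visits with the smallest residual variance, which would be the late ones.

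What is at stake is the standard error of the early treatment differences, chiefly Day 3. Table 14.2.14 is marked for the top-line results, so its visit-wise estimates will be read.

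**Working it through.** **1. Figures in the plan.** Neither document states an SD, slope or precision for the MMRM. The only sizing figure concerns the primary chi-square test, and it reproduces: odds ratio (0.22/0.78)/(0.07/0.93) = 3.747, power 80.2% at N = 202, and 202/0.96 = 210.4 against 210 planned. It does not depend on the MMRM.

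**2. Inputs.** From the documents: 140 and 70 patients, four post-baseline VAS visits, the model above. Assumed, because the documents give nothing: baseline SD 20 mm; the visit SDs shown in the table; correlation with baseline 0.1 to 0.6 (falling over visits, or constant at 0.5 or 0.3); residual AR(1) correlation 0.3 or 0.6; complete data.

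**3. Formulas.** Let b_t be the slope of the visit-t score on baseline, S the residual covariance matrix and 1 a vector of ones.
- Common slope: b = (1'S⁻¹b_t)/(1'S⁻¹1), a weighted mean of the visit slopes.
- Variance ratio at visit t, common over visit-specific slope: 1 + (b_t − b)² × var(baseline) / residual variance at t.

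**4. One case in full.** Visit SDs 14/7/3/2 mm, correlation 0.5 throughout, AR(1) 0.3.
- Slopes (0.5 × SD_t/20): 0.35, 0.175, 0.075, 0.05.
- Residual variances (0.75 × SD_t²): 147, 36.75, 6.75, 3.
- Weights: 0.008, 0.019, 0.215, 0.758. Common slope 0.0028 + 0.0033 + 0.0161 + 0.0379 = 0.060, close to the Day 29 value.
- Day 3: 1 + (0.29² × 400)/147 = 1.229.
- Day 8: 1 + (0.115² × 400)/36.75 = 1.144.
- Day 15: 1 + (0.015² × 400)/6.75 = 1.013.
- Day 29: 1 + (0.01² × 400)/3 = 1.013.

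**5. Variance ratios over the grid.**

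| Assumed VAS SDs, mm (Days 3/8/15/29) | Day 3 | Day 8 | Day 15 | Day 29 |
|---|---|---|---|---|
| 15/10/6/4 or 14/7/3/2 | 1.04–1.52 | 1.02–1.18 | 1.00–1.05 | 1.00–1.05 |
| 18/15/12/10 | 1.01–1.21 | 1.00–1.02 | 1.00–1.01 | 1.00–1.07 |
| 20 throughout, correlation falling | 1.01–1.06 | 1.00 | 1.01–1.02 | 1.01–1.06 |
| 20 throughout, correlation constant | 1.00 | 1.00 | 1.00 | 1.00 |

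In standard errors the largest values are √1.52 = 1.23 at Day 3, √1.18 = 1.09 at Day 8 and √1.07 = 1.03 at Day 29.

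**6. Why Day 3 tops out near 50% here.** If the common slope falls to 0, adjustment at Day 3 vanishes and the ratio becomes 1/(1 − r²), with r the correlation of the Day 3 score with baseline: 1.56, 1.33 and 1.10 for r = 0.6, 0.5 and 0.3. The steep cases come close to these limits.

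**7. Sensitivity to baseline SD.** With slopes and residual SDs held, the excess scales with the square of the baseline SD. In step 4, halving it to 10 mm turns 0.229 into 0.057. A steeper case goes higher: slopes 0.6/0.35/0.15/0.075, residual SDs 12/9/7/5.5 mm, residual correlation 0.4 between all visits, common slope 0.098. With baseline SD 20 mm it gives 1 + (0.502² × 400)/144 = 1.70 at Day 3 and 1 + (0.252² × 400)/81 = 1.31 at Day 8. With 10 mm it gives 1.18 and 1.08. The 20 mm version implies a Day 3 correlation with baseline of 0.71 (0.6 × 20/√(144 + 144)), above the grid.

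**8. Simulation** (140/70, SDs 15/10/6/4, 4,000 runs per scenario, with and without a floor at 0). Empirical variance ratios at Day 3 were 1.37–1.41, 1.25–1.29 and 1.07 for Day 3 correlations 0.6, 0.5 and 0.3; at Day 8 they were 1.01–1.07. The fitted coefficient on the change scale was −0.92 to −0.98, so Day 3 was nearly an unadjusted comparison. The mean treatment differences were practically the same under both models (for example −2.92 and −2.94 mm at Day 3). Model standard errors tracked the empirical SDs: 2.07 against 2.06 without the floor, 1.76 against 1.82 with it, for the common-slope model at Day 3. In a separate simulation of 1,500 trials per scenario, type I error was about 5% with either model.

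**The case against.** The strongest reply is that this is a legitimate model for exploratory endpoints and that any loss is hypothetical. Much of that stands.

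- **Size.** No document shows that VAS spread shrinks or that slopes differ; with equal slopes the loss is nil. Entry requires anterior chamber cells but no pain, and Protocol 2.1 cites 55% of patients with no pain or discomfort after this surgery and 5% with moderate to severe pain. Low baseline scores with little spread are therefore possible, and they would make the loss small.
- **Other analyses.** The SAP has a fallback: "If it is not possible to apply a MMRM due to the non-normality of the variable, the Mann Whitney Wilcoxon test will be performed". If scores pile up at 0 this may well be used, and the slope question then disappears. SAP 6.1 also adds a t-test or rank test of VAS score at each visit in Table 14.2.14. Neither is described as baseline-adjusted, so neither recovers the lost precision.
- **Day 8.** The documents single out Day 8, not Day 3, and there the loss is modest.

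A reader might also infer that the common slope biases the estimates by correcting baseline imbalance wrongly. Under randomisation the chance imbalance averages to zero, and its mis-correction is the same variance loss, not a second harm. SAP section 5 and the table list do place these MMRMs in the FAS non-RM set, which drops rescued patients after randomisation. A systematic imbalance there, multiplied by the slope error, could shift a Day 3 estimate. But the documents give no rescue rates and no link between rescue and baseline pain, and dropping rescued patients is a separate problem that this term would not cure.

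**Conclusion.** The omission is clear from the text and the mechanism is exact. The size is conditional. If VAS spread shrinks and the baseline slope flattens from Day 3 to Day 29, the variance of the Day 3 treatment difference is about 1% to 50% larger than the collected data require. The excess is usually below 20% at Day 8 and at most about 7% (3% in standard error) at Days 15 and 29. These ranges rest on assumed SDs, slopes and correlations and are not hard limits; more extreme inputs exceed them, as step 7 shows.

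The documents do not support reading this as an established loss, as an equal problem at Days 3 and 8, or as a threat to a confirmatory result: the primary and key secondary analyses are chi-square tests at Day 8. Nor does the argument carry over to BCVA, which has no Day 3 assessment and for which no drift towards a floor is described. The term is worth adding because it costs almost nothing. Priority is minor.

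**What to change.** In SAP 6.3.6.2, add the baseline-by-visit interaction to the MMRM for VAS photophobia and VAS pain (Tables 14.2.12 and 14.2.14), and say so in SAP 6.5. The cost is three slope parameters with four post-baseline visits, about 0.3% or less in standard error at 210 patients, and no new data. If the slopes turn out equal, almost nothing is lost.

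For consistency the term may be added to the BCVA model (Table 14.2.13; two parameters for three visits), but no precision gain has been shown there. In the diary model a baseline-by-day term costs one parameter per additional diary day, so it should be a separate decision.

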2. INTRODUCTION

2.1 Background

Global estimates suggest that 94 million people are visually impaired because of cataracts, and of these, 20 million are blind (1). Because the incidence of cataracts increases with age, an increase in the elderly population will lead to a significant increase in cataract prevalence. Cataracts currently affect approximately 26 million Americans (2), and approximately 25% of people in the United States of America (US) aged 65 to 69 years have cataracts, a proportion increasing to more than 68% of those aged over 80 years (3).

Cataract surgery is one of the most common surgical procedures performed worldwide. In fact, in 2017, 3.8 million cataracts procedures were performed in the US. The range of different types of procedures in ophthalmic surgery is broad, and the profile and characteristics of patients are widely varied (healthy young children, elderly patients and patients with multiple concomitant diseases and even neonates). The phacoemulsification technique was introduced in the treatment of cataract in 1967 and gained acceptance in the early 1990s when safety and efficacy improved. The efficacy of the phacoemulsification technique and the increase in life expectancy are the reasons for the increasing number of procedures performed.

Despite of surgical advances, pain and inflammation after ophthalmic surgery continues to be a burden on both patients and physicians (4). Postoperative inflammation is manifested principally as bulbar and ciliary hyperemia, corneal edema and aqueous cells and flare. The treatment of postoperative pain is essential for hospitalized patients, but it is even more important for patients who are treated on an outpatient basis (5).

Although cataract extraction is common, little is known about postoperative recovery and pain after phacoemulsification with intraocular lens implantation. However, knowledge of the postoperative complaints associated with ophthalmic surgery is necessary because these complaints may delay recovery and may significantly influence quality of life after the procedure (6).

The postoperative pain after this procedure was studied and found that 55% of patients had no pain or discomfort postoperatively, 32% reported slight discomfort, 8% of patients experienced mild pain and only 5% suffered moderate to severe pain (5,7).

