- (Proportion of patients with VAS pain score of "0-0.4 cm" (no eye pain) compared to placebo at Day 3, Day 8, Day 15 and Day 29)
- In table 14.2.14 both treatment groups (Clobetasol Propinate/Placebo) at each study visit will be compared using t-test or Mann Whitney Wilcoxon test, as applicable for VAS score.

For FAS non-Rescue and FAS populations.

Additional tables to cover these objectives for both populations 14.2.19.1, 14.2.19.2, 14.2.20.1 and 14.2.20.2 will be added.

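### An undefined non-normality switch lets an unadjusted Mann-Whitney test replace the baseline-adjusted MMRM for VAS pain, VAS photophobia and BCVA, losing the planned adjusted difference and its confidence interval

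*SAP*

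**What the plan says.** Protocol 9.1.12 sets the analysis of the continuous secondary endpoints: "treatment comparison will employ a mixed model of repeated measures (MMRM) with treatment as fixed factor and baseline as a covariate". The output is to include an estimate "of the adjusted treatment difference and 95% confidence interval". It has no non-parametric alternative.

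SAP 6.3.6.2 keeps that model and details it: "The model for analysis will include the change from baseline as a dependent variable, the baseline score as a cavariate", with treatment, visit, their interaction and an unstructured covariance. Failure to converge has its own remedy, which is to try other covariance structures and compare AIC. A separate sentence follows: "If it is not possible to apply a MMRM due to the non-normality of the variable, the Mann Whitney Wilcoxon test will be performed".

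SAP 6.5 ties baseline adjustment to the model: "Baseline value will be used as a covariate in the MMRM analyses for the continuous secondary efficacy endpoints". For Table 14.2.14 (change in VAS pain, flagged top-line), SAP 6.1 adds that the two arms "at each study visit will be compared using t-test or Mann Whitney Wilcoxon test, as applicable for VAS score". SAP 6.1 also says that the SAP supersedes the protocol's statistical methods.

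On status, SAP 6.3.6.2 states: "All secondary efficacy endpoints defined in this section will be analysed as exploratory". The primary and key secondary endpoints are tested by chi-square (SAP 6.3.5 and 6.3.6.1).

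**The concern.** Non-normality does not stop an MMRM from being fitted, and non-convergence is already covered. The switch therefore has an effect only if someone judges the distribution and decides that the model should not be used. The SAP does not say how, on which variable, at which visit or when. The blind review in SAP 6.2 is described as covering deviations and analysis sets, not distributions, so nothing written fixes the decision before unblinding.

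Once the switch is used, the plan specifies no baseline term and no effect estimate. A two-sample rank test also does not address the evolution over time that the paragraph sets out to compare. With no imputation (SAP 6.6), a patient who misses a visit drops out of that visit's test, whereas the MMRM would keep the patient's other visits.

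At stake is the reading of the continuous pain result. SAP 6.1 presents the added pain analyses as a consistency check on the dichotomous pain result. Such a check is weaker when the test, and possibly the quantity ranked, can be chosen after the data are seen.

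**Working it through.** **Inputs from the documents.** 140 vs 70 patients, two-sided alpha 0.05 (protocol 9.1 and 9.1.1). Pain after this surgery, from literature cited in protocol 2.1: "55% of patients had no pain or discomfort postoperatively", then 32% slight discomfort, 8% mild pain and 5% moderate to severe pain. The documents give no power, effect size, SD or baseline correlation for any VAS analysis; those below are assumptions. The only stated power belongs to the primary test, and it reproduces: 0.22 vs 0.07, 2:1, N = 202 gives 80.2% against the stated 80%.

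**Step 1: would a normality check fail?** Spread the four pain categories evenly over assumed bands of 0, 1–10, 10–30 and 30–80 mm. The mean is 0.32×5.5 + 0.08×20 + 0.05×55 = 1.76 + 1.60 + 2.75 = 6.1 mm. By simulation the SD is 13.0 mm and the skewness 3.4. Shapiro-Wilk at n = 210 rejected normality in all of 300 runs.

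**Step 2: normal-data benchmark.** Set ANCOVA at 80% power. The share of information that Mann-Whitney keeps is (3/π)(1−ρ²) on the score and (3/π)(1+ρ)/2 on the change. At ρ = 0.5 both equal 0.955×0.75 = 0.716, so power is Φ(2.802×√0.716 − 1.960) = Φ(0.411) = 66%. At ρ = 0.7 it is 50% (score) and 71% (change). With normal data the switch would not apply, so this is only a reference.

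**Step 3: the protocol's pain distribution.** 2,000 simulated trials per cell, latent effect 0.4 SD. A single-visit ANCOVA stands in for the MMRM visit contrast.

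| ρ | ANCOVA | Mann-Whitney, score | Mann-Whitney, change |
|---|---|---|---|
| 0.3 | 51% | 64% | 36% |
| 0.5 | 54% | 63% | 42% |
| 0.7 | 63% | 63% | 59% |
| 0.8 | 72% | 61% | 71% |

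With an assumed more painful baseline and the same effect, the figures were 61 / 68 / 27% at ρ = 0.5 and 76 / 69 / 36% at ρ = 0.8.

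**Step 4: against a rank test that keeps the baseline.** Zero-spiked VAS, 55% zeros on placebo at Day 8, latent effect 0.45 SD, 2,000 runs (Monte Carlo standard error at most √(0.25/2000) = 1.1 points).

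| Zeros at baseline | ρ | Rank ANCOVA | Mann-Whitney, change | Loss (points) |
|---|---|---|---|---|
| 35% | 0.3 | 73% | 30% | 43 |
| 35% | 0.5 | 78% | 36% | 42 |
| 35% | 0.6 | 80% | 42% | 38 |
| 55% | 0.3 | 72% | 44% | 28 |
| 55% | 0.5 | 76% | 51% | 25 |
| 55% | 0.6 | 82% | 61% | 21 |

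Mann-Whitney on the score had 72–75% in these runs. ANCOVA with robust standard errors (35% zeros at baseline) had 66, 71 and 74%. A further simulation under these assumptions, with ρ extended to 0.8, gave 74–93% for rank ANCOVA, 71–74% for Mann-Whitney on the score and 31–80% on the change. The loss against rank ANCOVA is then about 2 to 12 points on the score for ρ from 0.3 to 0.6, and about 20 at 0.8. On the change it is about 13 to 44 points.

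Under the null, every method rejected in about 4–6% of runs.

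**The case against.** Two stronger readings are tempting, and the documents support neither.

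*That the switch is almost certain to be used.* The wording makes it conditional on the MMRM being impossible to apply, and an MMRM can be fitted to skewed data. The planned Tables 14.2.12 to 14.2.14 are still titled as MMRM. The pain percentages come from literature on a general surgical population at an unstated time, not from patients selected for at least 5 anterior chamber cells, and they say nothing about photophobia. What stands is conditional: if a distribution check decides, VAS pain is likely to fail it.

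*That the switch throws away most of the power.* That needs the change to be ranked and a painful, variable baseline. If the score is ranked, Mann-Whitney matches or beats robust-error ANCOVA up to a correlation of about 0.5. SAP 6.3.6.2 does not say which is ranked. Its dependent variable is the change, while SAP 6.1 refers to the VAS score.

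Other points in the plan's favour also stand. SAP 6.5 does not contradict the switch, because it limits the covariate to the MMRM analyses. The SAP 6.1 test is added to the MMRM and does not replace it. A top-line flag is not confirmatory status. The simulations show no type I error problem for any single test; inflation from choosing among tests was not measured.

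These points limit the size of the problem. They do not supply a trigger, a ranked quantity or an effect estimate.

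**Conclusion.** The point holds as a weakness in the specification of exploratory analyses. The trigger and the ranked quantity are undefined, and the fallback loses the baseline adjustment and the difference with CI that the protocol promises. A second by-visit test with no selection rule sits in the same top-line table. No confirmatory conclusion is at risk.

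The power ranges rest on assumed effects, correlations, VAS bands and zero proportions, and on a single-visit stand-in for the MMRM. What does not depend on one scenario is that the answer can differ about twofold with a choice the SAP leaves open: at 35% baseline zeros and ρ = 0.5, 36% if the change is ranked against 72–75% if the score is. The change is worth making because it is nearly free and uses baseline data already collected.

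**What to change.** 1. Delete the non-normality sentence in SAP 6.3.6.2. Keep the MMRM as the analysis of VAS pain, VAS photophobia and BCVA whatever the distribution, and always report the adjusted difference with its 95% CI. Robust (sandwich) standard errors are a reasonable option.
2. Replace the Mann-Whitney and t-test clauses in SAP 6.1 and 6.3.6.2 with one pre-specified supportive test per visit: rank ANCOVA on the Visit 1 value, ranking the visit score.

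Step 1 secures the estimate and removes the data-dependent choice. It is not a power gain in itself, since robust-error ANCOVA can trail Mann-Whitney on the score at low correlation. The power gain comes from step 2.

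The cost is two SAP sentences and a few lines of code, with no new data. The drawback is that a rank test gives a p-value without an effect in VAS units, so it should stand beside the MMRM estimate and not replace it.
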